5.2 Primary Effectiveness Endpoint

Ability to adequately retract the colon and, as needed, peri-colorectal tissue and/or adjacent organs to achieve an effective exposure of the target tissue.

Adequate retraction will be deemed to be achieved if it is not necessary to use another port to insert another instrument to retract the target tissues.

Other Outcome Assessments

- Operative time
- Number of ports/incisions, and as compared to surgeon's standard of care (SOC) for this surgery type
- Time spent in the Post Anesthesia Care Unit (PACU)
- Length of stay (LOS) (time from admittance to post-anesthesia care unit until hospital discharge)
- Conversion rate (conversion to an open procedure due to inadequate MSS performance)
- Estimated blood loss
- Surgical Site Infection (SSI) rates

- Device malfunctions
- Subject satisfaction
- Investigator satisfaction with the MSS's ability to retract intended tissues and facilitate visualization of surgical site

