6 STUDY DESIGN

6.1 Overview

This is a prospective, multicenter, single-arm, open label study designed to assess the safety and effectiveness of the Levita Magnetic Surgical System in colorectal procedures.

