7.4 Procedure

The Investigator will perform the surgical procedure in accordance with the methods detailed in the Instructions for Use (IFU).

The following intra-operative data will be collected:

- General anesthesia time
- Operative time (from the first incision to the last suture's placement)
- Device and procedure observations
- Conversion to open surgical procedure and reason for conversion
- Number of ports utilized
- Number of ports typically utilized according to surgeon's SOC for specific surgical procedure
- The need for an additional port to place another retractor to retract the colon, peri-colorectal tissues or adjacent organs
- Estimated blood loss
- Video recording of the overall procedure
- Adverse events

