11 MONITORING AND QUALITY CONTROL PROCEDURES

11.1 Control of Systemic Error/ Bias

Clinical monitors will verify subject data and ensure compliance with Good Clinical Practices (GCPs), clinical protocol and other study requirements. As

detailed in Section 13, an Independent Physician will adjudicate all adverse events for relatedness, severity, and seriousness. The adjudication results will be used for purposes of data analysis. The Site Investigator's analysis will also be presented in the final clinical study report.

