11.2 Monitoring and Auditing

Monitoring visits to the clinical sites will be made periodically during the study, to ensure that all aspects of the current, approved protocol/amendment(s) are followed.

Prior to the enrollment of any subject in this study, site study personnel will be trained to Good Clinical Practice, the protocol and the device including Instructions For Use and management of a magnetic device. Additionally, the procedure for obtaining informed consent and the procedure for reporting adverse events will be reviewed.

Site monitoring visits will be performed by the Monitor on a regular basis during which case report forms will be 100% verified against source documentation. Data will be reviewed for safety information, legibility, completeness, accuracy, and logical consistency. Additional computer programs (e.g. edit checks) that identify selected protocol violations, out-of-range data, and other data errors may be used to help monitor the trial. Investigators will be required to make corrections to any data errors.

The Monitor is responsible for ensuring, through personal contact with the Investigator and site personnel, that the members of the clinical staff clearly understand and accept the obligations incurred in this investigation, and that these obligations are being fulfilled throughout the study. Specifically, the Monitor will interact with the site via telephone contact and periodic on-site visits to ensure that:

- Study facilities continue to be acceptable for the conduct of the study
- Regulatory and study documents are complete and current
- The protocol is appropriately followed
- Protocol amendments have been approved by the EC and the local regulatory authorities (as applicable), and the Sponsor has received the approval in writing
- Qualified subjects are enrolled in a timely manner
- Accurate, complete, and current records are maintained for all subjects
- The information recorded and submitted to the Sponsor is representative of the subject record and other supporting documentation
- Inconsistent and incomplete data are addressed and resolved
- Accurate, complete, and timely adverse event reports are being made to the Sponsor
- The site Principal Investigator continues to assume primary responsibility for the study
- Study devices are properly stored, dispensed, and accounted for

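### The primary effectiveness endpoint is scored on whether another retraction port was necessary, an undefined, unblinded judgement outside independent adjudication, rather than on whether one was used

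*Combined protocol and SAP*

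**What the plan says.** - **Endpoint.** Section 5.2, repeated in the synopsis, asks whether the colon and related tissue could be adequately retracted. It deems this achieved if "it is not necessary to use another port to insert another instrument to retract the target tissues". Neither necessity nor effective exposure is defined.
- **Data item.** Section 7.4 has the Investigator operate and lists among the intra-operative data: "The need for an additional port to place another retractor to retract the colon, peri-colorectal tissues or adjacent organs". The endpoint speaks of another instrument and the data item of another retractor.
- **Port counts.** Section 7.4 also collects the number of ports used and the number the surgeon would usually use for that operation. Neither enters the success rule.
- **Design.** Section 6.1 describes a "prospective, multicenter, single-arm, open label study"; Section 6.2 sets a target maximum of 30 subjects.
- **Bias control.** Section 11.1 provides that "an Independent Physician will adjudicate all adverse events for relatedness, severity, and seriousness". Section 13.1 gives the adjudicator the same remit. Effectiveness is in neither.
- **Monitoring.** Section 11.2 says "case report forms will be 100% verified against source documentation".
- **Video.** Section 7.4 lists "Video recording of the overall procedure". No reader, reading rule or effectiveness analysis is attached to it.

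**The concern.** The success rule scores an opinion about need when the underlying event, a port used for conventional retraction, can be observed. On the literal wording, an extra port that was used to retract target tissue but described as a convenience remains a success. The person best placed to make that call is the unblinded operator, who under Section 7.5 also rates satisfaction with the device.

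There is no control arm in which the same leniency would occur, so any lean is carried straight into the reported rate, and leniency can only raise it. Section 14.11 says the study may support regulatory submissions, where the question of how success was verified is to be expected. The plan already accepts the principle for safety: under Section 11.1 the adjudicated adverse event results are used for analysis and the site's own assessment is shown alongside. The primary effectiveness endpoint has no counterpart.

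**Working it through.** The plan states no success rate, performance goal, alpha or power (Section 9.2 says no formal sample size estimation was done), so there is no figure to reproduce. The check has three parts.

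**1. What one call is worth.** With n = 30, one subject is 1/30 = 3.3 percentage points. Exact (Clopper-Pearson) 95% limits for x successes are the 2.5% quantile of Beta(x, n − x + 1) and the 97.5% quantile of Beta(x + 1, n − x). For 30/30 the lower limit reduces to 0.025^(1/30) = 0.884.

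| Successes | Rate | Exact 95% CI |
|---|---|---|
| 30/30 | 100% | 88.4 to 100 |
| 29/30 | 96.7% | 82.8 to 99.9 |
| 28/30 | 93.3% | 77.9 to 99.2 |
| 27/30 | 90.0% | 73.5 to 97.9 |

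Two failures recorded as not needed turn 28/30 into 30/30: +6.7 points on the rate and +10.5 on the lower limit (88.4 − 77.9).

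**2. How a lean would show.** Let p be the true success rate and m the share of true failures coded as success. The observed rate is q = p + (1 − p)m, the expected count is 30q, and the chance of at least 29 successes is 30q^29(1 − q) + q^30. Both p and m are assumed; the documents give neither.

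| p | m | q | Expected of 30 | Chance of at least 29 |
|---|---|---|---|---|
| 0.90 | 0 | 0.900 | 27.0 | 18% |
| 0.90 | 0.25 | 0.925 | 27.8 | 33% |
| 0.90 | 0.50 | 0.950 | 28.5 | 55% |
| 0.80 | 0 | 0.800 | 24.0 | 1% |
| 0.80 | 0.25 | 0.850 | 25.5 | 5% |
| 0.80 | 0.50 | 0.900 | 27.0 | 18% |

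**3. Whether existing checks would catch it.**
- Source verification (Section 11.2) confirms that the form matches the source. If the source records that a port was not needed, the form agrees and the check passes.
- Adjudication (Sections 11.1 and 13.1) is triggered by adverse events, and an extra port is not in itself one.
- The port count is a real partial check, but its only comparator is the surgeon's usual number. Section 1.1 anticipates fewer ports with the device. If the usual number is k, the operation is planned with k − 1, and one retraction port is added, the count is k. That equals the usual number and flags nothing. The count becomes a check only if the planned ports are recorded too.

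**The case against.** The case for leaving the plan alone has substance.

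- **The ordinary reading is factual.** Most surgeons would take Section 5.2 to mean that no further port was used for retraction, and nothing suggests the looser reading is intended. That makes this partly a matter of wording, but the wording decides how a disputed case is scored.
- **The result can be cross-checked.** Port count, usual port count and conversion with its reason are recorded separately, and port number and conversion rate are reported as other outcomes. A reader might infer that this one item is all the effectiveness evidence, or that the report could never reveal leniency. Neither follows. What remains is that the count does not show why a port was placed.
- **The video is not shown to be idle.** A reader might infer that it is recorded and used for nothing. The documents support only that no use in effectiveness is specified. Section 13.1 gives the adverse event adjudicator all available data, and Section 11.2 does not exclude the video from source documentation.
- **The rater is not named.** A reader might take it as stated that the surgeon scores the endpoint. Section 7.4 names the Investigator as operator and does not say who records the port items, so this is a strong inference only.
- **No decision turns on it.** Section 9.1 plans description only. Moving from 28/30 to 30/30 crosses no threshold, and the two intervals overlap heavily. This limits severity but does not remove the bias.
- **Reading every video would be an added layer.** This stands. Section 7.4 does not say whether the recording shows port placement, so the remedy should not depend on it.

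**Conclusion.** The point holds as a defect in the success rule. Primary effectiveness rests on a necessity judgement with no criterion, in an open-label single-arm study whose independent adjudication is limited to adverse events. Each used-but-not-needed call is worth 3.3 points; two would lift 93.3% to 100%.

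This rests on three assumptions: the operating investigator makes the call; the literal wording could govern a disputed case; and the number of lenient calls, which is unknown and could be zero. The documents do not show that leniency will occur or that any conclusion would reverse. The change should be made because it is nearly free and removes a one-directional source of doubt from the primary effectiveness result. It is not a reason to regard the study as unsound.

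**What to change.** 1. **Score the fact.** In Section 5.2, the synopsis and Section 7.4, use one identical definition. Record the planned port set and each port's purpose before first incision. Count as a failure any port beyond that set, or any port placed at the outset for conventional retraction, through which a non-MSS instrument was used to retract target tissue, whatever need is stated. State that using a conventional grasper to reposition the Grasper Tip, which Section 2 allows, does not count.
2. **Cross-check.** Compare this item with the planned port set and the number of ports used, and report the number of discordant cases.
3. **Resolve discordant cases only.** Extend the Independent Physician Adjudicator's remit in Section 13.1 to these cases. Let the adjudicator consult the existing video where it shows the port or the retraction; otherwise report the case as not verifiable. The redaction rule in Section 10.1 applies to any recording that goes to the Sponsor.

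Cost: protocol wording, one pre-incision entry on the case report form and a small extension of the adjudicator's remit. No visit or procedure is added, and routine reading of all videos is not needed. The rule is deliberately strict: a port added for another reason and then used to retract target tissue is a failure. The reported success rate may therefore be slightly less favourable.

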5 STUDY ENDPOINTS

The following endpoints will be evaluated in all enrolled subjects who undergo colorectal procedures using the Magnetic Surgical System.

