6.2 Sample Size and Number of Centers

The study will be conducted at up to three (3) study sites with a target maximum of 30 subjects in which the Levita Magnetic Surgical System is used for colorectal procedures.

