8.2 Risks

There are risks associated with use of the Levita Magnetic Surgical System including:

- Electromagnetic field incompatibility or interference
- Malfunctioning of the device
- Breakage of the device
- Allergic reaction related to the device
- Abdominal wall/cavity/tissue and/or organ injury or damage (e.g. inflammation, redness)
- Infection
- Tissue damage, including hematoma, bleeding or petechiae
- Vascular injury
- Gastro-intestinal injury
- Organ perforation
- Need for extended surgery
- Additional surgical intervention due to any of the above factors (includes reoperation)

These adverse events do not include all adverse events, which occur with surgery in general, but are important considerations particular to laparoscopic instrumentation.

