9 STATISTICAL SECTION

9.1 Statistical Methods

Data collected in the study will be presented using various descriptive statistics. Descriptive summaries will be the basis of study reports to generate an overall summary of the safety and effectiveness for the device.

Descriptive tables will be produced for baseline characteristics including demographics and medical history.

Missing data on study endpoints will be described.

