9.2 Sample Size Justification

This is a single-arm, multicenter, investigational study. No formal sample size estimation has been performed. As safety and effectiveness have already been demonstrated in several prior indications (laparoscopic

cholecystectomy, bariatric and prostate procedures), it is expected that enrollment of 30 subjects will provide ample evidence of safe and effective use of the MSS in this additional subject population.

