12.6 Device Deficiency

All device deficiencies related to the identity, quality, durability, reliability, safety or performance (includes malfunctions, use errors, and inadequate labeling) of the device shall be documented. Sponsor will assess all device

deficiencies that could have led to a serious adverse device effect for potential regulatory reporting requirements.

In the event of a suspected malfunction or device deficiency, the study device should be returned to the Sponsor for analysis. Instructions for returning the study device will be provided by the Sponsor.

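### The conversion rate counts only conversions blamed on inadequate MSS performance, an undefined and unreviewed cause, so other conversions to open surgery may be left out of it

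*Combined protocol and SAP*

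**What the plan says.** Under the other outcome assessments in Section 5.2, the protocol lists "Conversion rate (conversion to an open procedure due to inadequate MSS performance". This is the only conversion outcome named. Neither Section 5 nor the statistical section names an all-cause rate or a breakdown by reason.

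Data collection is wider. Section 7.4 records "Conversion to open surgical procedure and reason for conversion" for each operation, with no restriction on cause.

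The population is set in Section 5: "The following endpoints will be evaluated in all enrolled subjects who undergo colorectal procedures using the Magnetic Surgical System". Section 6.2 gives the size as a "target maximum of 30 subjects in which the Levita Magnetic Surgical System is used for colorectal procedures". On analysis, Section 9.1 says "Data collected in the study will be presented using various descriptive statistics", and Section 9.2 says "No formal sample size estimation has been performed".

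Sections 11.1 and 13.1 give the Independent Physician Adjudicator the adverse events to review. The reason for a conversion is not part of that remit.

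**The concern.** The outcome is a subset of the conversions that occurred, selected by a causal judgement. The protocol does not define inadequate performance of the MSS, does not say who decides whether a conversion meets it, and provides no independent review of that decision. The study is open label with a single arm, so there is no blinding or concurrent control to steady the judgement. Two sites could classify the same case differently.

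The excluded cases matter. Section 8.2 names "Tissue damage, including hematoma, bleeding or petechiae" among the risks of using the system, along with vascular injury, gastro-intestinal injury and organ perforation. An operation converted for one of these may or may not be counted, depending on how the undefined term is read. An operation converted because of adhesions or difficult anatomy would probably not be counted.

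A low or zero conversion rate could then be read as the proportion of operations that ended open, which it is not. Section 14.10 anticipates publication, and Section 14.11 says the study may support regulatory submissions, so the figure is likely to be read outside the study team.

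**Working it through.** The documents state no conversion rate, so there is no figure of the plan's own to reproduce. The check has two parts: where each kind of conversion would appear under the text as written, and how far the restricted and all-cause rates could differ at the planned size.

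**Where each conversion appears.** The first three columns follow from Sections 5.2 and 7.4, the last from Sections 5.1, 11.1, 12.1.1 and 13.1.

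| Reason for conversion | Recorded (7.4) | In the defined rate (5.2) | Reported and adjudicated as an adverse event |
|---|---|---|---|
| MSS does not retract adequately | Yes | Yes | Only if an adverse event also occurred |
| Bleeding or injury | Yes | Unclear, because the term is undefined | Yes |
| Adhesions or anatomy | Yes | Probably not | Possibly not, as there may be no adverse event |

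The third row is the weakest point. Such a conversion may appear in no summary that the protocol names. Section 7.1.2 excludes a subject whose anatomy, seen after the operation has begun, prevents device use. The anatomy cases at issue are therefore those in which the MSS was used.

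**Size.** The input is n = 30 (Section 6.2). The counts x below are assumptions for illustration.

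- One conversion omitted: 1/30 = 3.3 percentage points.
- Exact (Clopper-Pearson) 95% limits: the lower limit is the 2.5% quantile of Beta(x, n − x + 1), and the upper limit is the 97.5% quantile of Beta(x + 1, n − x). For x = 0 the lower limit is 0 and the upper limit is 1 − 0.025^(1/30) = 0.1157.

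| x of 30 | Rate | Exact 95% CI |
|---|---|---|
| 0 | 0% | 0 to 11.6% |
| 1 | 3.3% | 0.1 to 17.2% |
| 2 | 6.7% | 0.8 to 22.1% |
| 3 | 10.0% | 2.1 to 26.5% |

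A restricted result of 0/30 can stand beside any of the lower rows as the all-cause result.

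**Would there be conversions to omit?** For an assumed all-cause probability p, the chance of at least one conversion in 30 is 1 − (1 − p)^30, and the expected number is 30p.

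| Assumed p | Expected conversions | Chance of at least one |
|---|---|---|
| 2% | 0.6 | 45% |
| 5% | 1.5 | 79% |
| 10% | 3.0 | 96% |
| 15% | 4.5 | 99% |

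Over this range the chance that the definition has at least one conversion to classify runs from about even to near certain.

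**The case against.** The strongest reply is that little is actually hidden. All conversions and reasons are collected, and Section 9.1 promises descriptive presentation of the data collected, so a full listing would be within the plan. Bleeding, vascular injury and perforation are adverse events. They fall under the primary safety endpoint, and their relation to the device is judged by an independent physician whose results are used in the analysis. The procedure is video recorded, and Section 11.2 has case report forms fully verified against source, so the recorded reason can be audited. A device-specific rate also suits a device evaluation, and leaving adhesions out of a measure of device failure is defensible. Finally, this is one of several unranked outcomes, with no hypothesis test or success criterion attached.

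Much of this stands, and it limits the point. A general promise of descriptive statistics, however, does not override an explicit restricted definition of the named outcome. Video and source verification leave a record but do not define the cause or assign anyone independent to judge it. Adverse event reporting does not reach a conversion that involved no adverse event.

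A reader might infer three stronger things, none of which the documents support:

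- That the operating surgeon assigns the cause. Section 7.4 collects the reason as intra-operative data and no other route is named, which makes site attribution likely, but the text does not say so.
- That device-caused injury is definitely outside the rate. Section 12.6 refers to "All device deficiencies related to the identity, quality, durability, reliability, safety or performance", which names safety and performance as different items. That list describes device deficiencies. It does not set up exclusive categories and does not define the term in Section 5.2. A grasper that tears tissue could be argued to have performed inadequately.
- That device-caused harm escapes reporting or independent review. It does not, for the reasons above.

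**Conclusion.** The concern holds as a modest reporting defect. The only named conversion outcome is filtered by an undefined cause that is not independently reviewed, so it may understate how many operations were converted to open surgery. At n = 30 the understatement is 3.3 points per omitted conversion. A gap of 0% against 10.0% would require three omitted conversions, which is an assumed figure and not a prediction. The conclusion rests on the wording of Sections 5.2 and 7.4 and on the limits of the adjudicator's remit. It does not depend on any particular conversion rate. Because the outcome is descriptive and no decision rule uses it, the defect affects how the result will be read and does not threaten the study's main conclusions. It should be corrected, since the data needed are already being collected.

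**What to change.** In Section 5.2, define the outcome as conversion to open surgery for any reason, with all subjects in whom the MSS was used as the denominator. Tabulate it by the reason recorded under Section 7.4 in three groups: inadequate MSS retraction, injury or bleeding, and other. Report the MSS-attributed rate as a subset of the total, so that the sponsor's own measure is kept.

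The cost is revised wording and one table. No new data are needed. The headline conversion rate may be higher than under the present definition.
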